- If clinical remission (achieved at E5 1311.6) has been lost after end of treatment in 1311.6 and/or at screening for 1311.20/M15-989, patients will receive open label i.v. re-induction treatment with three infusions of 600 mg each every 4 weeks after which eligibility will be re-assessed. If clinical remission or at least response compared to 1311.6 study baseline (V2) is achieved patients will switch to s.c. maintenance treatment with 180 mg s.c. every 8 weeks ([Flow chart 3](#)), otherwise an EoT visit has to be performed. After last administration of trial drug in 1311.20/M15-989 trial, a 140 day follow up call should be scheduled for patients who do not elect to enroll in Study M16-000.
- If clinical response (achieved at E1 or E5 1311.6) has been lost after end of treatment in 1311.6 and/or at screening for 1311.20/M15-989, patients will receive open label i.v. re-induction treatment with three infusions of 600 mg each every 4 weeks after which eligibility will be re-assessed. If clinical response or remission compared to 1311.6 study baseline (V2 1311.6) is achieved patients will switch to s.c. maintenance treatment with 180 mg s.c. every 8 weeks ([Flow chart 3](#)), otherwise an EoT visit has to be performed. After last administration of trial drug in 1311.20/M15-989 trial, a 140 day follow up call should be scheduled for patients who do not elect to enroll in Study M16-000.

The results from the last colonoscopy done in 1311.6 will serve as baseline for 1311.20/M15-989. A colonoscopy at screening is only required for patients who lost

response or remission during extended follow-up phase after completion of 1311.6. Colonoscopies are repeated once per year to assess the effect of continued treatment on endoscopic response and mucosal healing.

The end of study is defined as the date the last subject completes the End of trial visit

The primary analysis will be performed after all patients have completed their EoT visit. The reference values for the efficacy endpoints clinical or endoscopic response will be the baseline values in 1311.6.

For details regarding Adverse event and serious adverse event reporting, see [Section 5.2.2.2](#)

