Description of change	
1. Figure 3.1:1: Legend: "1311.6" changed to "1311.20"
 
2. Added: "... an 8 weeks OR 5 times the half-life (whichever is longer) wash-out period..."
 
3. Added: If clinical response or remission (CDAI drop ≥ 100 from baseline of 1311.6 or CDAI < 159) was maintained after end of treatment ... (FLOW CHART 1) (visit window between last IMP dose in 1311.6 and first IMP dose in 1311.2 should be at least 8 weeks), deleted: "Flow Chart 2"
 
4. Added: "If clinical response or remission compared to 1311.20 study entry OTHERWISE VISIT EoT HAS TO BE COMPLETED 15 WEEKS after last administration of trial drug..."
 
5. Deleted: "response or" 2x
 
6. Added : "(achieved at E5 1311.6)", "or at least response compared to 1311.6 study entry baseline (V2)"
 
7. Replaced "1311.20 study entry" to "1311.6 study baseline (1311.6 V2)"
 
8. Added: "If clinical response (achieved at E1 or E5 1311.6) has been lost after end of treatment in 1311.6 and/or at screening for 1311.20, patients will receive open label i.v. re-induction treatment with three infusions of 600 mg each every 4 weeks after which eligibility will be re-assessed. If clinical response or remission compared to 1311.6 study baseline (V2 1311.6) is achieved patients will switch to s.c. maintenance treatment with 180 mg s.c. every 8 weeks (Flow chart 3), otherwise visit EoT has to be completed 15 weeks after last administration of trial drug in 1311.20 trial."

Rationale for change	
1. Typos
 
2. Typos
 
3. Change of Flowchart number for and additional explanation regarding treatment visit window added.
 
4. Additional explanations regarding eligibility of patients
 
5. Additional statement about patient who lost response was added
 
6. Additional clarifications on eligibility reassessment were added
 
7. More broad criteria for eligibility reassessment at Visit 5
 
8. Additional clarification added for patients who lost response

Section to be changed	Section 3.3.2 Inclusion Criteria
Description of change	
1. Added: "... (drop in CDAI from baseline by ≥ 100) AND/or remission..."

Number of global amendment		1.0

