5.0 Analysis Populations

5.1 Definition of Analysis Populations

5.1.1 Efficacy Populations

Intent-to-Treat Analysis Set

The Intent-to-Treat Analysis Set (ITT) includes all subjects who received at least one dose of risankizumab in the current study.

- The Intent-to-Treat Analysis Set for IV (ITT_IV) includes all subjects who received at least one dose of risankizumab IV in the current study.
- The Intent-to-Treat Analysis Set for SC (ITT_SC) includes all subjects who received at least one dose of risankizumab SC in the current study.

The ITT population will primarily be used for all efficacy analyses. Any by-period analyses on IV (or SC treated population) will be based on ITT IV set (or ITT SC set).

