6.4 Definition of Visit Windows

Since subjects do not always adhere to the study visit schedule, the following rules will be applied to assign actual visits to protocol-specified visits including early termination visits. For each study visit mentioned in the protocol, a nominal or target day will be selected to represent the corresponding visit along with a window around the target day. Windows will be selected in a non-overlapping fashion so that a date collected on the case

report form (CRF) does not correspond to multiple visit windows. Moreover, windows will not discard any post-baseline measurement recorded on the CRF. If a subject had 2 or more actual visits in one visit window, the visit closest to the target will be used as the study visit for that window. If two visits are equidistant from the target day, then the later visit will be used for reporting.

The visit windows and the target/nominal day for each study visit are shown in the tables below. The visit windows defined below will be based on relative days to either first dose on IV or first dose on SC.

Table 1. Windows for subcutaneous injection period for ITT_SC (SA_SC) population, using for Vital sign, Lab Values, Fistula exam, CDAI, Review patient diary (PRO data).

Nominal Visit Week^d	Lower Bound	Nominal Day	Upper Bound
0	-999	1 ^a	1
8	2	57	85
X ^c	$1 + 7*(X - 4) + 1$	$1 + 7*X$	$1 + 7*(X + 4)$
200	1374	1401	9999 ^b

- a. Day of first dose of study drug for subcutaneous injection.
- b. It is minimum of (the last dose date + 140 days, the first dose date of Study M16-000 sub-Study 3) for the subjects who entered the Study M16-000 sub-Study 3; otherwise it is the last dose date +140 days.
- c. $X = 8*i$, $i = 2, \dots, 24$.
- d. Nominal visit week is a transformation of the protocol-specified week. For the patients' schedule following the Flow Chart 1, nominal visit week = protocol-specified week – 4. For the patients' schedule following the Flow Chart 2, nominal visit week = protocol-specified week – 6. For the patients' schedule following the Flow Chart 3 (only for subcutaneous injection period), nominal visit week = protocol-specified week – 16.

Table 2. Windows for subcutaneous injection period for ITT_SC population, using for CDEIS and SES-CD.

Nominal Visit Week ^c	Lower Bound	Nominal Day	Upper Bound
0	-999	1 ^a	1
48	2	337	533
104	534	729	897
152	898	1065	1233
200	1234	1401	9999 ^b

- a. Day of first dose of study drug for subcutaneous injection.

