- d. Nominal visit week is a transformation of the protocol-specified week. For the patients' schedule following the Flow Chart 1, nominal visit week = protocol-specified week - 4. For the patients' schedule following the Flow Chart 2, nominal visit week = protocol-specified week - 6. For the patients' schedule following the Flow Chart 3 (only for subcutaneous injection period), nominal visit week = protocol-specified week - 16.
- e. Since some fecal calprotectin data at screening visit are loaded into the last visit of the feeder Study M15-993, the combined fecal calprotectin data from the feeder Study M15-993 and the current Study M15-989 will be used to derive the value at Week 0.

Table 5. Windows for subcutaneous injection period for ITT_SC population, using for hs-CRP.

Nominal Visit Week ^d	Lower Bound	Nominal Day	Upper Bound
0	-999 ^e	1 ^a	1
8	2	57	113
X ^c	1 + 7*(X - 8) + 1	1 + 7*X	1 + 7*(X + 8)
120	786	841	869
128	870	897	925
136	926	953	985
152	986	1065	1093
160	1094	1121	1177
176	1178	1233	1261
184	1262	1289	1345
200	1346	1401	9999 ^b

- a. Day of first dose of study drug for subcutaneous injection.
- b. It is minimum of (the last dose date + 140 days, the first dose date of Study M16-000 sub-Study 3) for the subjects who entered the Study M16-000 sub-Study 3; otherwise it is the last dose date + 140 days.
- c. $X = 8 + 16*i$, $i = 1, 2, 3, 4, 5, 6$.
- d. Nominal visit week is a transformation of the protocol-specified week. For the patients' schedule following the Flow Chart 1, nominal visit week = protocol-specified week - 4. For the patients' schedule following the Flow Chart 2, nominal visit week = protocol-specified week - 6. For the patients' schedule following the Flow Chart 3 (only for subcutaneous injection period), nominal visit week = protocol-specified week - 16.
- e. Since some hs-CRP data at screening visit are loaded into the last visit of the feeder Study M15-993, the combined hs-CRP data from the feeder Study M15-993 and the current Study M15-989 will be used to derive the value at Week 0.

Table 6. Windows for IV injection period for ITT_IV (SA_IV) population, using for Vital sign Lab Values, Fistula exam, CDAI, Review patient diary (PRO data)

Nominal Visit Week ^b	Lower Bound	Nominal Day	Upper Bound
0	-999	1 ^a	1
4	2	29	43
8	44	57	71

- a. Day of first dose of study drug for IV injection.

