9.0 Efficacy Analysis

9.1 General Considerations

There is no formal statistical hypothesis test planned. Descriptive analyses will be used to analyze the proportion of participants achieving the efficacy endpoints. The study is designed to gain extensive documentation of safety and efficacy.

9.1.1 Analysis of Efficacy Endpoints by Variable Type**9.1.2 Missing Data Imputation for Efficacy Endpoints**

Missing data imputation will be done only for categorical efficacy variables. For the analysis other than efficacy, no imputation will be done for missing values.

Non-Responder Imputation (NRI)

The NRI approach is used for binary efficacy variables. These variables can take values of 'Achieved' or 'Not Achieved' or may be missing for any reason including discontinuation from study. According to the NRI imputation approach, all missing values will be considered as 'Not Achieved.' If a subject has missing value for a specific visit, the data will be imputed using NRI only for the period which the visit belongs to.

Observed Case (OC)

Observed case analysis will be performed, i.e., missing values will not be imputed. An analysis using only the observed data will be performed as a sensitivity analysis for primary and secondary efficacy endpoints.

Imputation of Missing Dates

For baseline, efficacy, and safety parameters, if the day and/or month are missing, the following conventions will be used to impute the missing dates:

- 01 for missing start day
- End of month for missing end day
- January 1st for missing start month
- December 31st for missing end month

In case of partially missing AE start and stop dates, the dates will be imputed by comparing to first dose date of study medication so that the corresponding AEs will be made treatment-emergent whenever possible. If the start date of an AE is partially

missing and the month is the same as the start date of a new therapy, the AE will be made treatment emergent to the new therapy.

In case of missing or partially missing study drug dosing dates, the dates will not be imputed. Subjects will be treated as not receiving dose on that date.

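### SAP Table 6 stops at IV day 71 with no Week 12 row, so results after the full re-induction course, and the post-course values of patients who fail it, fall in no IV by-visit window

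*SAP*

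**What the plan says.** **Course and reassessment.** Patients who lost response or remission follow Flow Chart 3. Protocol 3.1 gives them "three infusions of 600 mg each every 4 weeks after which eligibility will be re-assessed". Those who regain at least a response move to s.c. treatment; "otherwise an EoT visit has to be performed". Flow Chart 3 places the infusions at Visits 2, 3 and 4 (protocol Weeks 4, 8 and 12) and the first s.c. dose at Visit 5 (Week 16). Its footnote 7 puts assessments before dosing.

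**Windows.** Table 6 in SAP 6.4 is the only window table for the IV period: "Windows for IV injection period for ITT_IV (SA_IV) population, using for Vital sign Lab Values, Fistula exam, CDAI" and diary data. Its rows are Week 0 (up to day 1), Week 4 (days 2-43, nominal 29) and Week 8 (days 44-71, nominal 57). Footnote b subtracts 4 from the protocol week. Tables 1 to 5, for the SC period, each end in an open row; Table 6 does not.

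**General rules.** SAP 6.4 says its rules "assign actual visits to protocol-specified visits including early termination visits" and that "windows will not discard any post-baseline measurement recorded on the CRF".

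**Populations and imputation.** SAP 5.1.1 bases IV-period analyses on ITT_IV. The SC set ("ITT_SC) includes all subjects who received at least one dose of risankizumab SC in the current study") needs an SC dose. Under SAP 9.1.2, for a missing visit, "the data will be imputed using NRI only for the period which the visit belongs to".

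**The concern.** The visit that shows what three infusions achieved is Visit 5, and Table 6 has no place for it. Its last row is measured before the third infusion.

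Patients who go on to s.c. treatment keep their Visit 5 value, but as SC Week 0 in ITT_SC, mixed with patients who were never re-induced. Patients who fail have no SC dose, so Tables 1 to 5 do not apply to them, and their later values lie past Table 6's last bound.

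The by-visit output therefore cannot show CDAI response, CDAI remission, PRO-2 or fistula results after the full course with every IV-treated patient in the denominator, and the patients left out are those who did badly. The proportion who never moved to SC can be recovered from set counts as (ITT − ITT_SC)/ITT_IV, but the clinical results behind it cannot. By-visit laboratory and vital-sign summaries have the same hole.

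**Working it through.** **1. Reproduce Table 6.** IV nominal week = protocol week − 4; nominal day = 1 + 7 × week.

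| Visit | Protocol week | IV week | Nominal day | Infusions already given | Row in Table 6 |
|---|---|---|---|---|---|
| 2 | 4 | 0 | 1 | 0 | yes |
| 3 | 8 | 4 | 29 | 1 | yes |
| 4 | 12 | 8 | 57 | 2 | yes |
| 5 | 16 | 12 | 85 | 3 | **no** |

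The printed bounds follow the midpoint rule: (29 + 57)/2 = 43 and (57 + 85)/2 = 71. The second midpoint needs a Week 12 target at day 85, so the table is built as if that row followed. Visit 5's nominal day is 85 − 71 = 14 days past the last bound.

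**2. Can the permitted visit windows bring Visit 5 into the Week 8 row?** Flow Chart 3 allows, in days from Week 0:

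- Visit 2: 28 ± 7 = 21 to 35
- Visit 4: 84 ± 5 = 79 to 89
- Visit 5: 112 ± 7 = 105 to 119

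Relative to the first infusion (difference + 1):

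- Visit 5, earliest: 105 − 35 + 1 = day 71
- Visit 5, latest: 119 − 21 + 1 = day 99
- Visit 5 if Visit 2 is on time: 105 − 28 + 1 = day 78 to 119 − 28 + 1 = day 92

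Of the 29 days from 71 to 99, 28 lie beyond Table 6.

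**3. The remaining day.** Day 71 needs Visit 2 at +7 and Visit 5 at −7 together. Visit 4 is then on day 79 − 35 + 1 = 45 to 89 − 35 + 1 = 55, which is 2 to 12 days from the target of 57. Visit 5 is 71 − 57 = 14 days away. SAP 6.4 takes the closer visit, so Visit 4 is used.

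Across all timings, 15 × 11 × 15 = 2,475. Visit 5 falls on day 71 in 11 of them and is selected in 0. This assumes that Visit 4 yields a usable value; if it does not, a day-71 Visit 5 could stand in for Week 8.

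**4. Where the Visit 5 value goes.**

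- *Continues to SC:* protocol Week 16 − 16 = SC Week 0, in Table 1 on ITT_SC/SA_SC.
- *Fails re-induction:* not in ITT_SC/SA_SC, and past day 71 in Table 6, so in no by-visit row. The protocol does not date the EoT visit relative to Visit 5; a later EoT is further outside still.
- *NRI:* no IV Week 12 visit is defined, so nothing can be imputed there. After IV Week 8 a failure is counted as not achieving the endpoint in no windowed table.

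**5. Compare with the SAP's other IV-period limits.** IV exposure (SAP 8.2.1) runs to the earlier of last IV dose + 28 days and first SC dose: on schedule 57 + 28 = day 85. IV patient-years (SAP 10.2.1.7) and IV concomitant medication (SAP 7.3) run to the earlier of last IV dose + 140 days and first SC dose. Only the by-visit windows close at day 71.

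**The case against.** The strongest reply is that little hangs on this. The primary objective is long-term safety, efficacy is descriptive with no primary endpoint or test, and no listed endpoint is a re-induction response rate. All of that is true and limits the importance of the point. But response, remission and PRO-2 by visit are listed secondary endpoints, and the SAP itself assigns IV-period analyses to ITT_IV.

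A second reply is that the values survive elsewhere. For patients who continue, starting the SC period at Visit 5 is coherent. The final observation in SAP 6.2 would include a failure's last value, and the full ITT set includes failures. However, the SAP names no by-visit efficacy table that uses the final observation, and it gives no windows for the full ITT set. Treatment-emergent adverse events, laboratory shift tables, CTC Grade 3 or higher listings and potentially significant values do not depend on Table 6 and are not in question.

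Third, the protocol wording that names the reassessment visit ("More broad criteria for eligibility reassessment at Visit 5") comes from the amendment log. The argument does not need it: Protocol 3.1 puts reassessment after three infusions, and s.c. dosing starts at Visit 5.

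Finally, a table row might have been lost in converting the PDF. That cannot be excluded entirely, but Table 6 runs straight into its footnotes with no sign of a gap.

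**Conclusion.** The concern holds. As written, Table 6 contradicts SAP 6.4's own statements on early termination visits and on not discarding data. No by-visit table shows the outcome of the full re-induction course in everyone who received it.

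With Visit 4 attended and usable, the Visit 5 value enters an IV by-visit summary in 0 of 2,475 permitted timings. These are counts of combinations, not probabilities. The number of patients concerned is unknown: the documents give approximately 60 enrolled but not how many were re-induced or failed, so it may be small.

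This should be corrected, but it does not threaten the primary safety objective. It concerns analysis windows only and takes no position on the dosing or continuation rules.

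**What to change.** Add a row to Table 6:

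| Nominal week | Lower bound | Nominal day | Upper bound |
|---|---|---|---|
| 12 | 72 | 85 | First SC dose date (pre-dose values); if no SC dose, last IV dose date + 140 days |

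- Report CDAI, PRO-2, fistula, laboratory and vital-sign summaries at IV Week 12 on ITT_IV/SA_IV, with NRI for the binary efficacy endpoints.
- Keep the same value as SC Week 0 for patients who continue. Amend SAP 6.4 to say that a value may serve in both periods but only once within a table. Table 1's Week 0 row, open from day −999, already reaches back into the IV period.
- State how a Visit 5 on day 71 is handled. The lower bound of 72 follows the SAP's midpoint rule and leaves that case in Week 8, where NRI could then score an observed Week 12 result as missing. Assigning Visit 5 by its scheduled visit would close the gap.

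The cost is one table row, a sentence or two of text and some programming. All the data are already collected.

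A separate small item in the same section: in Table 5 the cut between Weeks 136 and 152 is 985/986, whereas the midpoint is (953 + 1065)/2 = 1009. The other 13 post-baseline cuts follow the midpoint rule, so 1009/1010 looks intended. It affects only off-schedule samples.

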7.1.1 Analysis of Demographic Data and Baseline Characteristics

Demographic and Baseline characteristics will be summarized with descriptive statistics. The number of non-missing observations, mean, standard deviation, median, minimum and maximum will be summarized for continuous variables. Categorical or discrete variables will be summarized by counts and percentages.

7.2 Medical History

Medical history data will be summarized using primary Medical Dictionary for Regulatory Activities (MedDRA) system organ classes (SOCs) and preferred terms (PTs) for each treatment group according to Version 18.0 or higher of the MedDRA coding dictionary. The SOCs will be presented in alphabetical order, and the PTs will be presented in alphabetical order within each SOC. A subject who reports 2 or more different PTs, which are in the same SOC, will be counted only once in the SOC total. Subjects reporting more than one condition for a given PT will be counted only once for that term. No statistical comparison will be performed on medical history.

7.3 Previous Treatment and Concomitant Medications

The number and percent of subjects who received concomitant medication listed below will be tabulated by the generic name assigned by the most current version of the World Health Organization (WHO) Drug Dictionary in alphabetical order for concomitant medications. The prior medication, which is defined as any medication taken prior to the first dose of current study drug, has been reported in the feeder Study M15-993 and will not be evaluated here. No statistical comparisons will be performed.

A concomitant medication is defined as any medication other than study drug and the rescue medication that (1) was started prior to the first dose of study drug and continued to be taken after the first dose of study drug or (2) was started after the first dose of study drug, but was not started after the last dose of study drug. The definition of a concomitant medication for each of IV period and SC period can be defined similarly using the first dose of study drug in that period and the last dose of study drug in that period. A particular medication will be classified as "prior" or "concomitant" or "both" according to the rules provided in [Table 7](#), where "FD" is the date of the first dose of study drug and "LD" is the date of last dose of study drug plus 140 days.

Table 7. Rules for Prior and Concomitant Medication Classification

Medication		Medication Stop Date					
Start Date	Ongoing?	Missing	< FD	= FD	(FD, LD)	= LD	> LD
Missing	YES	1, 2					
	NO/Missing	1, 2	1	1, 2	1, 2	1, 2	1, 2
< FD	YES	1, 2					
	NO/Missing		1	1, 2	1, 2	1, 2	1, 2
= FD	YES	2					
	NO/Missing			2	2	2	2
(FD, LD)	YES	2					
	NO/Missing				2	2	2
= LD	YES	2					
	NO/Missing					2	2
> LD	YES	3					
	NO/Missing						3

- 1 = Prior, 2 = Concomitant, 3 = Post-treatment.
- "FD" is the date of the first dose of study drug.
- "LD" is the date of last dose of study drug plus 140 days.

Concomitant medications at baseline of Study M15-989 include prior medications that have a start date before first dose of study drug of Study M15-989 and are ongoing or have a stop date after first dose of study drug of Study M15-989.

Particularly, a concomitant medication for IV period should have the start date before the date of last dose of study drug in IV period plus 140 days or the date of the first dose in SC period, whichever occurs earlier. A concomitant medication for SC period should have the start date before the date of last dose of study drug in SC period plus 140 days or the date of the first dose in Study M16-000 sub-Study 3 if any, whichever occurs earlier.

